1 INTRODUCTION

This document describes the statistical analysis for protocol D5290C00003, a pivotal Phase 2b study to determine if MEDI8897 is efficacious in reducing medically attended respiratory syncytial virus (RSV)-confirmed lower respiratory tract infection (LRTI) in healthy preterm infants entering their first RSV season. The primary efficacy hypothesis of

this study is that, compared to placebo, a single 50-mg intramuscular (IM) dose of MEDI8897 will be efficacious in reducing medically attended LRTI caused by RT-PCR-confirmed RSV in healthy preterm infants born between 29 weeks 0 days and 34 weeks 6 days gestational age (GA) and entering their first RSV season, and the safety profile will be acceptable. The secondary hypotheses are that (1) there will be a reduction in the incidence of hospitalizations attributable to RSV, (2) the predicted extended $t_{1/2}$ will be adequate for the duration of the RSV season, and (3) ADA to MEDI8897 will not significantly impact the serum concentrations or safety of MEDI8897 over the 5-month RSV season. These hypotheses will be assessed by the incidence of RSV LRTI, RSV hospitalization, ADA, pharmacokinetics parameters, and descriptive statistics from safety data. This document details the statistical summaries relating to each study objective and describes the general conventions and definitions that will be used.

In addition, a set of table templates and specifications is planned to be created in a statistical programming plan to complement this document.

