1.6 Research Hypotheses

1.6.1 Primary Hypothesis

Compared to placebo, a single ■ mg IM dose of MEDI8897 will be efficacious in reducing medically attended LRTI caused by RT-PCR-confirmed RSV in healthy preterm infants born between 29 weeks 0 days and 34 weeks 6 days gestational age (GA) and entering their first RSV season, and the safety profile will be acceptable.

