1 INTRODUCTION

This document describes the statistical analysis plan (SAP) for protocol D5290C00003, a pivotal Phase 2b study to determine if MEDI8897 is efficacious in reducing medically attended respiratory syncytial virus (RSV)-confirmed lower respiratory tract infection (LRTI) in healthy preterm infants entering their first RSV season. The primary efficacy hypothesis of this study is that, compared with placebo, a single 50-mg intramuscular (IM) dose of MEDI8897 will be efficacious in reducing medically attended LRTI caused by reverse transcriptase-polymerase chain reaction (RT-PCR)-confirmed RSV in healthy preterm infants born between 29 weeks 0 days and 34 weeks 6 days gestational age (GA) and entering their first RSV season, and the safety profile will be acceptable. The secondary hypotheses are that (1) there will be a reduction in the incidence of hospitalizations attributable to RSV, (2) the predicted extended terminal half-life ($t_{1/2}$) will be adequate for the duration of the RSV season, and (3) anti-drug antibodies (ADA) to MEDI8897 will not significantly impact the serum concentrations or safety of MEDI8897 over the 5-month RSV season. These hypotheses will be assessed by the incidence of RSV LRTI, RSV hospitalization, ADA, pharmacokinetic (PK) parameters, and descriptive statistics from safety data. This document details the statistical summaries relating to each study objective and describes the general conventions and definitions that will be used.

In addition, a set of table templates and specifications is planned to be created in a statistical programming plan to complement this document.

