2.1.2 Secondary Study Objectives

1. To assess the efficacy of MEDI8897 for the reduction of hospitalizations due to RT-PCR-confirmed RSV, compared with placebo
2. To evaluate the safety and tolerability of MEDI8897 when administered as a single fixed IM dose, compared with placebo
3. To evaluate single-dose serum concentrations of MEDI8897

4. To evaluate ADA responses to MEDI8897 in serum

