3 STATISTICAL METHODS

3.1 General Considerations

Summary statistics will be tabulated by treatment group. Categorical data will be summarized by the number and percentage of subjects in each category. Continuous variables will be summarized by mean, median, standard deviation, minimum, and maximum. In general, unless stated otherwise, baseline will be defined as the last non-missing value prior to dosing.

There are two planned analyses for this study: the Primary Analysis and the Final Analysis. The Primary Analysis will be conducted after all randomized subjects have completed the Day 151 visit. At the time of this primary analysis, approximately half of all subjects enrolled (722 subjects) will have completed the Day 361 visit. The remaining 731 subjects will have completed approximately 8 months of the study. MEDI8897’s efficacy will be evaluated in the Primary Analysis as intended by the study design. In addition, all available PK, ADA, and safety data will be analyzed. The final analysis will be conducted when all subjects have completed the last visit of the study.

Data analyses will be conducted using the SAS® System Version 9.3 or higher (SAS Institute Inc., Cary, NC) in a SAS GRID environment.

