3.7.1 Adverse Events and Serious Adverse Events

Adverse events will be coded by MedDRA version 19 or higher and the type, incidence, severity and relationship to study investigational product will be summarized by treatment group. Specific AEs will be counted once for each subject for calculating percentages. In addition, if the same AE occurs multiple times within a particular subject, the highest

severity and level of relationship observed will be reported. All treatment-emergent AEs (TEAEs) will be summarized overall, as well as categorized by MedDRA SOC and PT.

Additional summaries will present TEAEs by SOC, high-level term, SOC, and high-level group term. Nontreatment-emergent AEs/serious adverse events (SAEs) will be presented in the listings.

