3.7.2 Adverse Events of Special Interest

Adverse events of special interest (AESI) will include targeted AEs of hypersensitivity (including anaphylaxis), thrombocytopenia, and immune complex disease (eg, vasculitis, endocarditis, neuritis, glomerulonephritis), and the type, incidence, and relationship to study investigational product will be summarized by treatment group and by SOC and PT based on MedDRA. Additional groupings may be added by the Medical Monitor, if warranted.

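### Safety is to be compared with placebo, but the SAP plans only counts and percentages by arm, so for rare events the report would not show what excess the data exclude

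*SAP*

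**What the plan says.** Secondary objective 2 in SAP v5 Section 2.1.2 is "To evaluate the safety and tolerability of MEDI8897 when administered as a single fixed IM dose, compared with placebo". The primary hypothesis (protocol 1.6.1, repeated in SAP v5 Section 1) ends "and the safety profile will be acceptable", and neither document defines acceptable.

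The sentence in the SAP Introduction on how the hypotheses are assessed ends "pharmacokinetics parameters, and descriptive statistics from safety data" in SAP v3 and "pharmacokinetic (PK) parameters, and descriptive statistics from safety data" in the current SAP v5. The substance is the same.

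The SAP v5 convention in Section 3.1 is "Categorical data will be summarized by the number and percentage of subjects in each category". For adverse events, Section 3.7.1 says "the type, incidence, severity and relationship to study investigational product will be summarized by treatment group". For AESIs, Section 3.7.2 says "the type, incidence, and relationship to study investigational product will be summarized by treatment group". Sections 3.7.3 (skin reactions) and 3.7.4 (new onset chronic disease) follow the same pattern, as does protocol 4.8.4. None of them names a between-arm difference, ratio, interval or margin.

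The only statement on safety precision is in Section 2.4. With 1,000 infants on MEDI8897 it gives a 90% chance of at least one event at a true rate of 0.2%, and an upper bound of 0.3% if no event is seen. Both figures concern one arm.

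**The concern.** The objective is comparative, but the planned output leaves the comparison to the reader's eye. For common adverse events that does little harm. For rare ones, two similar percentages carry little information, particularly with a placebo arm half the size of the active arm. A table showing 0.5% against 0.4% looks reassuring, yet the same data may be compatible with a several-fold excess.

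The single-arm statement in Section 2.4 helps only when no event occurs on MEDI8897: the excess cannot be larger than the rate itself, so a bound on the rate also bounds the excess. Once events occur, it says nothing about the excess over placebo.

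Safety exposure also set the size of this trial: Section 2.4 attributes the 1,500 infants to the request for 1,000 exposed, and efficacy power already exceeds 99%. The aim that fixed the sample size thus has no planned between-arm estimate.

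**Working it through.** **The plan's own figures (Section 2.4, n = 1,000 on MEDI8897).**
- Upper bound with no events: 1 - 0.05^(1/1000) = 0.299%. This agrees with the stated 0.3% and is a one-sided bound.
- Chance of at least one event at 0.2%: 1 - 0.998^1000 = 86.5%, against the stated 90%. Reaching 90% needs a rate of about 0.23% or 1,151 infants. This is a separate discrepancy, and nothing below depends on it.

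**Inputs for the comparison.** Section 3.1 gives 722 + 731 = 1,453 infants. Assuming a 2:1 split, 1,453 × 2/3 ≈ 969 on MEDI8897 and 484 on placebo. The documents give no expected rates for these events, so the counts below are assumptions covering a range.

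**Risk difference, Miettinen-Nurminen 95% limits.** Solve for d in
(x1/n1 - x2/n2 - d) / sqrt{[p1(1-p1)/n1 + p2(1-p2)/n2] × N/(N-1)} = ±1.96,
where p1 and p2 are the maximum likelihood estimates constrained to p1 - p2 = d, and N = n1 + n2.

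- 5/969 vs 2/484: 0.516% - 0.413% = +0.10 points. At the upper limit p1 = 1.066%, p2 = 0.202% and the standard error is 0.388 points: (0.103 - 0.864)/0.388 = -1.96. At the lower limit p1 = 0.381%, p2 = 1.392% and the standard error is 0.568: (0.103 + 1.011)/0.568 = 1.96. **95% CI -1.01 to +0.86.**
- 10/969 vs 5/484: 1.032% - 1.033% = 0.00 points. Upper limit: p1 = 1.641%, p2 = 0.590%, standard error 0.537. Lower limit: p1 = 0.810%, p2 = 2.248%, standard error 0.733. **95% CI -1.44 to +1.05.**
- 0/969 vs 0/484: at the upper limit p2 = 0, so apart from the N/(N-1) factor d = 1.96²/(969 + 1.96²) = 3.84/972.84 = 0.395%. **Upper limit +0.40 points.** Most of the gap from 0.3% arises because this limit is two-sided and the Section 2.4 bound is one-sided.

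**Relative risk, Wald limits on the log scale.** SE = sqrt(1/x1 - 1/n1 + 1/x2 - 1/n2).
- 5 vs 2: RR = 1.25, SE = sqrt(1/5 - 1/969 + 1/2 - 1/484) = 0.835. Limits 1.25 × exp(±1.96 × 0.835) = **0.24 to 6.4**.
- 10 vs 5: RR = 1.00, SE = 0.545. Limits **0.34 to 2.9**.

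**How the uncertainty shrinks with more events.** Exact conditional limits at the planned 1000/500, with perfectly balanced counts (observed RR = 1):

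| Events (MEDI8897 vs placebo) | 95% CI for RR |
|---|---|
| 4 vs 2 | 0.14 to 11.1 |
| 10 vs 5 | 0.31 to 3.7 |
| 20 vs 10 | 0.45 to 2.4 |
| 100 vs 50 | 0.71 to 1.4 |

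The last row works as follows. Of 150 events, 100 are on MEDI8897, with Clopper-Pearson limits for that share of 0.585 and 0.741. Dividing the odds by the allocation ratio of 2 gives 0.585/0.415/2 = 0.71 and 0.741/0.259/2 = 1.43. Exact limits are somewhat wider than Wald limits (for 10 vs 5, an upper limit of 3.7 against 2.9), but the message is the same.

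**The case against.** The plan delivers the safety endpoint as defined. Protocol 2.2.2 defines it as the occurrence of events, and a side-by-side table against a concurrent randomised placebo arm is a comparison of a kind. The SAP says openly that safety is assessed descriptively, and no passage promises an interval or a test. Descriptive safety reporting is common and is not in itself an error. That stands: the point concerns a better output for the stated objective, not a breach of the protocol.

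The plan also contains more than incidence by arm. It covers severity and relationship (3.7.1), age and weight subgroups (3.7.5), timing from dosing (3.7.6) and anti-drug antibody status (3.8). The protocol provides a monitoring committee (4.8.7) and suspension criteria (4.4). For a rare AESI, case review may weigh more than a ratio. These safeguards are real, but none of them reports a comparative estimate. Anyone could compute the intervals from the published counts, so no data are lost; the SAP simply does not commit to showing them. Table templates are deferred to a programming plan outside these documents, so intervals may yet appear there.

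Two stronger readings are tempting. A reader might infer that similar percentages would lead to the safety part of the primary hypothesis being accepted. The documents contain no acceptance rule for safety, so that cannot be said. A reader might also cite the trial's limited power to detect a multiple of a rare background rate. That follows from sample size and allocation, and adding intervals would not change it.

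**Conclusion.** The point holds as a reporting gap limited to rare events. The current SAP sets a comparison with placebo as an objective, plans number and percentage by arm, and states precision for one arm only. With a handful of events per arm, the data would leave open an absolute excess of roughly 0.4 to 1.05 percentage points. In relative terms the upper limits are about 3 (10 vs 5 events) to 6 (5 vs 2), and the report would not show this. By 100 vs 50 events the upper limit on the relative risk is about 1.4, so common adverse events are not a concern.

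The sizes rest on assumed event counts and on a 2:1 split of 1,453 infants. The As-treated numbers may differ slightly, but using 1000/500 barely changes the limits. The absence of any between-arm safety interval in the SAP does not depend on these assumptions.

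**What to change.** In SAP v5 Sections 3.7.1, 3.7.2 and 3.7.4, add the risk difference (MEDI8897 minus placebo) with a Miettinen-Nurminen 95% CI on the As-treated population for:
- deaths
- any SAE
- TEAEs of Grade 3 or higher
- related TEAEs
- each AESI category
- new onset chronic diseases

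Plan no p-values and no decision rule. Without an agreed margin, an upper limit does not define acceptable, so the intervals should inform the safety statement and not decide it. Extend the Section 1 sentence to name these differences and intervals, and require that any statement comparing safety with placebo is reported with them.

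The SAP already plans exact conditional intervals for sparse efficacy counts (Sections 3.5.1.6 and 3.5.1.7), so interval estimation on few events is not new to it. The change needs no additional test, alpha or sample size. The cost is a few extra columns, and intervals for rare events that will be wide and may look less reassuring than bare percentages.

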2 STUDY OVERVIEW

2.1 Study Objectives

2.1.1 Primary Study Objective(s)

To assess the efficacy of MEDI8897 when administered as a single 50 mg IM dose to healthy preterm infants born between 29 weeks 0 days and 34 weeks 6 days GA and entering their first RSV season for the reduction of medically attended LRTI due to RT-PCR-confirmed RSV, compared to placebo.

2.1.2 Secondary Study Objectives

1. To assess the efficacy of MEDI8897 for the reduction of hospitalizations due to RT-PCR-confirmed RSV, compared to placebo
2. To evaluate the safety and tolerability of MEDI8897 when administered as a single fixed IM dose, compared to placebo
3. To evaluate single-dose serum concentrations of MEDI8897
4. To evaluate ADA responses to MEDI8897 in serum

2.1.3 Exploratory Study Objectives

To assess healthcare resource utilization (HRU) and caregiver burden for MEDI8897 recipients compared to placebo recipients.

2.2 Study Design

The population to be enrolled is healthy preterm infants born between 29 weeks 0 days and 34 weeks 6 days GA who would not receive RSV prophylaxis based on the AAP or other local or national guidelines. These infants will not be receiving palivizumab, allowing for a placebo comparator group for the determination of efficacy and the safety profile. A total of 1,500 infants will be randomized 2:1 to receive a 50 mg IM dose of MEDI8897 (N = 1000) or placebo (N = 500). Randomization will be stratified by temperate zones in the northern and southern hemisphere and by subject age group at randomization (ie, ≤ 3 months, > 3 to ≤ 6 months, > 6 months). Enrollment of infants > 6 months of age will be limited to approximately 500. All infants will be followed for approximately 360 days after dosing.

2.3 Treatment Assignment and Blinding

An IWRS will be used for randomization to a treatment group and assignment of blinded investigational product kit numbers. A subject is considered randomized into the study when the investigator notifies the IWRS that the subject meets eligibility criteria and the IWRS provides the assignment of blinded investigational product kit numbers to the subject.

Subjects will be randomized at a 2:1 ratio to receive a 50 mg IM dose of MEDI8897 (N = 1,000) or placebo (N = 500). Randomization will be stratified by temperate zones in the northern and southern hemisphere and by subject age group at randomization (ie, ≤ 3 months, > 3 to ≤ 6 months, > 6 months). Enrollment of infants > 6 months of age will be limited to approximately 500.

The procedure for using IWRS is as follows:

- The investigator or designee contacts the IWRS and provides the SID number and subject's baseline characteristic(s) used to verify that it is the same subject
- Placebo (provided by site) or a vial from a MEDI8897 kit will be assigned to the subject
- Confirmation of this information is sent to the unblinded investigational product manager who prepares the investigational product to be dispensed to the subject per the response system and records the appropriate information in the investigational product accountability log

Investigational product (MEDI8897 or placebo) must be administered the same day the investigational product is assigned. Total in-use storage time from needle puncture of the investigational product vial to administration should not exceed 4 hours at room temperature. If storage time exceeds these limits, a new vial should be used. If there is a delay in the administration of investigational product such that it will not be administered within the

specified timeframe, the unblinded investigational product monitor must be notified immediately.

2.4 Sample Size

The sample size of 1,500 is necessary based on advice from the US FDA requesting that 1,000 preterm infants be exposed to MEDI8897 in this Phase 2b study. This sample size has approximately > 99% power to detect 70% relative risk reduction, assuming a placebo group medically attended RSV LRTI incidence of 8%. Power calculations are based on Poisson regression model with robust variance (Zou, 2004) comparing MEDI8897 50 mg versus placebo, with 2-sided, $\alpha = 0.05$.

- The 70% relative risk reduction assumption is based on a placebo-controlled study in Native American infants in which there was 87% relative reduction in the incidence of RSV hospitalization (11.3% placebo; 1.5% motavizumab; $p < 0.001$) and 71% relative reduction in the incidence of outpatient RSV LRTI (10.0% placebo; 2.9% motavizumab; $p < 0.001$) in infants who received motavizumab prophylaxis (O'Brien et al, 2015)

In order to evaluate risk, a sample size of 1,000 subjects exposed to MEDI8897 will provide a 90% probability of observing at least one AE if the true event rate is 0.2%; if no AEs are observed, this study provides 95% confidence that the true event rate is < 0.3%.

3 STATISTICAL METHODS

3.1 General Considerations

Summary statistics will be tabulated by treatment group. Categorical data will be summarized by the number and percentage of subjects in each category. Continuous variables will be summarized by mean, median, standard deviation, minimum and maximum. In general, unless stated otherwise, baseline will be defined as the last non-missing value prior to dosing.

There are two planned analyses for this study: the Primary Analysis and the Final Analysis. The Primary Analysis will be conducted after all randomized subjects have completed the Day 151 visit. At the time of this primary analysis, approximately half of all subjects enrolled (722 subjects) will have completed the Day 361 visit. The remaining 731 subjects will have completed approximately 8 months of the study. MEDI8897's efficacy will be evaluated in the Primary Analysis as intended by the study design. In addition, all available PK, ADA, and safety data will be analyzed. The final analysis will be conducted when all subjects have completed the last visit of the study.

Data analyses will be conducted using the SAS® System Version 9.3 or higher (SAS Institute Inc., Cary, NC) in a SAS GRID environment.

3.2 Analysis Populations and Datasets

The analysis populations are defined in [Table 3.2-1](#).

Table 3.2-1 Analysis Populations

Population	Description
Intent-to-treat (ITT) population	Subjects who are randomized will be included in the ITT population; in this population data will be analyzed according to their randomized treatment group.
As-treated population	Subjects who are randomized and receive any study investigational product will be included in the as-treated population; in this population, data will be analyzed according to the treatment they actually receive.
Per-protocol population	The per-protocol population includes subjects in the ITT population who receive the correct dose of randomized treatment and who do not have a serious protocol violation. Detailed criteria defining this population will be determined and documented prior to performing the Primary Analysis.

Analysis Datasets

- The Primary Dataset contains all data (efficacy, safety, ADA, PK) from all randomized subjects through the Day 151 visit and all available safety data as of the data cutoff date. The Primary Analysis will be performed on the Primary Dataset.
- The Final Dataset contains all data collected in this study, including data in the Primary Dataset and data from the subjects who were ongoing at the time when the Primary Dataset was locked. The Final Analysis will be performed on the Final Dataset.

3.3 Stratification Factors

Two stratification factors are used in study design as well as in data analysis, and these are: age group at randomization [age ≤ 3 months (ie, age ≤ 91 days), age > 3 to ≤ 6 months (ie, age > 91 to ≤ 183 days), age > 6 months (ie, age > 183 days)] and hemisphere (northern hemisphere, southern hemisphere). For subjects who were assigned to an incorrect age stratum at randomization, the age stratum as calculated from the electronic case report form (eCRF) will differ from the stratum recorded for the subject in the IWRS database. Unless stated otherwise, the age stratum based on the CRF calculation will be used.

CRF calculation for age when full DOB is available:

- Age at randomization (months) = (randomization date – date of birth) / (365.25/12)

When full DOB is unavailable, age at screening will be used. Since screening may be collected in terms of days, weeks, or months, it will be first converted in terms of months as follows:

- Age at screening (days) / (365.25/12) = Age at screening (months)
- Age at screening (weeks) / (52/12) = Age at screening (months)

Once Age at screening is converted to months,

- Age at randomization (months) = Age at screening (months) + [(randomization date – screening date) / (365.25/12)]

Determination of hemisphere in stratification and analysis is as follows. The sites have been grouped together by country into the following two hemispheres: Northern Hemisphere (Belgium, Bulgaria, Canada, Czech Republic, Estonia, Finland, France, Hungary, Italy, Latvia, Lithuania, Poland, Spain, Sweden, Turkey, United Kingdom, and USA) and Southern Hemisphere (Argentina, Australia, Brazil, Chile, New Zealand, and South Africa).

